5. CONCEPTUAL FRAMEWORK AND OPERATIONALIZATION

Figure 1 shows how project activities (inputs) will lead to outputs and result in outcomes as well as the potential impact of the planned activities. The model shows the combined activities planned within study 1 and study 2.

[figure not shown]

Figure 1: Logic model for the CIFF/IAF programme that includes the two studies presented in this protocol

The objectives of the programme intervention and the indicators to assess achievement of these objectives are shown in Table 1.

Table 1: Objectives and corresponding key indicators

Level of data	Hypothesis	Indicators	Proposed studies
Purpose 1: To assess the effect of the 1AF intervention package on birth outcomes, anemia, micronutrient deficiencies, stunting, and morbidity in mothers and their young children			
Impact	Decreased stunting in children receiving the intervention package (or parts thereof)	
 • Change in length-for-age z scores (LAZ) • Percentage of children whose LAZ is below -2 standard deviations from the median of the WHO Child Growth Standard 	• Study 1&2
Impact	Reduced prevalence of anemia and micronutrient deficiencies in children receiving the intervention package	
 • Change in proportion with anaemia • Change in haemoglobin concentration • Change in retinol binding protein concentration (i.e. vitamin A status) • Change in concentration of serum ferritin and soluble transferrin receptor (i.e. iron status) 	• Study 1
Impact	Increased birth weight of children from mothers having received the intervention package during the pregnancy	
 • Change in birth weight 	• Study 1
Outcome	Reduced prevalence (or incidence) in diarrheal disease in infants and young children receiving the intervention package	
 • Age- and sex-specific morbidity rates with a focus on diarrhoea 	• Study 1
Purpose 2: To identify and assess the conceptual and operational factors at the different stages of the intervention package that may have affected the outcome			
Outcome	Increased intake of nutritional products among pregnant and lactating women and children	
 • Consumption of adequately formulated nutritional products in the period preceding data collection • Monitoring of type, frequency and quantity of adequate nutritional products 	• Study 1&2

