In round 2, interview questions related to diet and nutrition KAP during pregnancy, dietary diversity, antenatal care, and WASH will be asked. Additionally, MUAC (mid-upper arm circumference) will be measured and a capillary blood sample for measurement of haemoglobin concentration, malaria parasitaemia and micronutrient status will be provided.

Round 3 (Within 24-48 hours after delivery):

The mother-child pair will be visited within 24-48 hours after delivery. The following information will be recorded: delivery date and time, delivery method, recent antenatal care, and early initiation of breastfeeding. The mother will be assessed for MUAC but no blood sampling will be conducted. For the newborn, head circumference, birth weight and birth length, and haemoglobin concentration (from a heelprick) will be measured.

Round 4 (At 6.5 mo ± 1 mo of age of offspring):

This assessment will be conducted when the child turns 6.5 months old. Breastfeeding and other infant and young child feeding indicators, child morbidity, maternal dietary diversity, postnatal care, and WASH information will be gathered. In mothers, MUAC and weight will be measured and haemoglobin concentration and malaria parasitaemia from a capillary sample will be assessed. In

children, length, weight and head circumference will be measured and a capillary blood sample for haemoglobin concentration, malaria parasitaemia and micronutrient status will be provided.

Round 5 (At 24 ± 1mo of age of offspring):

This assessment will be conducted when the child turns 24 months old. Questionnaire-based information on child feeding, child dietary diversity, child morbidity and WASH will be collected. As in round 4, child length, weight and head circumference will be measured and a fingerprick blood sample will be provided for the measurement of haemoglobin concentration, malaria parasitaemia, and micronutrient status. No maternal biomarkers will be collected at this point.

As part of the monthly visits to the participants' households, the CHV will also collect data on intervention adherence and recent morbidity.

[figure not shown]

Figure 2: Timing of assessment rounds for study 1.

[figure not shown]

Figure 3: Detailed procedures for each assessment round in study 1

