7.2 Sample size and randomization

Study 1 and 2:

Some indicators included in study 1, such as maternal haemoglobin, child haemoglobin, and child length-for-age z score (LAZ), are measured more than once in the same study subject over time. This is also the case for haemoglobin and height-for-age z score (HAZ) in the children in study 2. For these indicators, the average change in outcomes in study subjects in the intervention group will be compared to the average change in study subjects in the control group. Other indicators in study 1, such as birth weight and length, are measured only once in each study subject. For these indicators, the average value in the intervention group will be compared to the average value in the control group.

The sample size depends on the size of the desired minimum difference between the intervention group and the control group, which can be detectable with statistical significance. This minimum

difference is expressed as the effect size, which is the difference in the value of the indicator between the two groups to be compared divided by the standard deviation of the indicator. For those outcomes measured more than once, the indicator is the change over time in study subjects. This effect size can be written as follows:

$$\frac{[\text{Mean}(LAZ_{C_x} - LAZ_{C_y})_{\text{Group1}} - \text{Mean}(LAZ_{C_x} - LAZ_{C_y})_{\text{Group2}}]}{\text{Standard deviation}(LAZ_{C_x} - LAZ_{C_y})_{\text{Group1}}}$$

Where C_x and C_y stand for the two measurements of those indicators which are measured twice.

The sample size calculations make the following assumptions: 1) a two-tailed comparison (that is, there is no *a priori* conclusion about which group is higher and which is lower), 2) statistical significance is defined as a p value less than 0.05, 3) the power of the study is at least 0.8, and 4) that the standard deviation of the indicator in both study groups is the same.

Although it is difficult to find highly comparable interventions and their effect sizes for key outcomes put forth, Table 5 below provides an overview of observed effect sizes for somewhat similar interventions and outcomes.

Table 5: Effect sizes in children for similar outcomes and interventions reported in the literature

Description of intervention	Reported outcome	Effect size (95%CI)	Reference
Maternal education on complementary feeding and provision of complementary foods	Weight gain	0.34 (0.11, 0.56)	[35]
	Linear growth	0.26 (0.08, 0.43)	

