7.3.3 Criteria for withdrawal/discontinuation of participants

Study 1:

Pregnant women are free to withdraw themselves or their children from participation in the study at any time. If the pregnant woman is being diagnosed with severe anaemia (haemoglobin (Hb)<70g/L) or severe acute malnutrition (MUAC < 23 cm) at round 1, she will be excluded from participation and will be referred for treatment according to national guidelines to the nearest health centre. If the pregnant woman is being diagnosed with malaria parasitaemia and has an axillary temperature of >37.5°C in round 1, she will be referred for treatment but will continue participating in the study after temporary suspension from interventions if required as assessed by the study physician. If the pregnant woman has an Hb between 70 and 109 g/L in rounds 1 or 2, she will be advised by the study team to go to the hospital for further management. This will be facilitated by CHVs. If the mother, infant or child is being diagnosed with malaria parasitaemia and an axillary temperature of >37.5°C, or severe anaemia (Hb<70g/L), or they suffer from severe acute malnutrition (WHZ<-3 and/or bilateral oedema for child, MUAC < 23 cm for mother) in rounds 2 to 5, affected participants will be referred for treatment according to national guidelines but will continue in the study after temporary suspension from interventions if required as assessed by the study physician. If a child is born with low birth weight (<2500 g) and/or has a Hb < 135 g/L, he/she will be referred for a medical check. Further, study participants will be discontinued from participation in the study in case of any clinical significant adverse event (AE), or any other medical condition or situation that prevents continued participation in the study. If a participant is discontinued no specific follow-up assessments will be conducted other than the follow up until resolution in case of exclusion due to a serious adverse event (SAE). Participants will not be replaced, as a non-consent and dropout rate of 46% prior to reaching 24 months of age is included in the sample size calculation.

Study 2:

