Blood-based secondary outcomes measured in children in study 1 include: Haemoglobin concentration measured at birth and 6 and 24 months of age will be used to assess the change in haemoglobin concentration and proportion with anaemia ($Hb < 11g/dL$). SF (serum ferritin), CRP (C-reactive protein) and AGP (alpha 1- acid glycoprotein) measured at 6 and 24 months of age will be used to assess the proportion with inflammation-adjusted iron deficiency ($SF < 12 \mu g/L$) and the change in proportion with inflammation-adjusted iron deficiency. RBP (retinol binding protein), CRP and AGP measured at 6 and 24 months of age will be used to assess the proportion with inflammation-adjusted vitamin A deficiency ($RBP < 0.7 \mu mol/L$) and the change of proportion with inflammation-adjusted vitamin A deficiency.

Blood-based secondary outcomes measured in pregnant women include: Haemoglobin concentration measured at 34 weeks gestation and 6 months postpartum will be used to assess the change in haemoglobin concentration, the proportion with anaemia ($Hb < 11 g/dL$), and the change in the proportion with anaemia. SF, CRP and AGP measured at 34 weeks gestation will be used to assess the proportion with inflammation-adjusted iron deficiency ($SF < 15 \mu g/L$). RBP, CRP and AGP measured at 34 weeks gestation will be used to assess the proportion with inflammation-adjusted vitamin A deficiency ($RBP < 0.7 \mu mol/L$).

The measurement of haemoglobin will be undertaken on-site using the HemoCue™ device and commercially available control blood. The control blood will be used every morning before measuring any participant's blood sample. SF, RBP, CRP and AGP will be measured using the enzyme linked immunosorbent assay (ELISA) technique at the VitMin laboratory in Germany which is using control samples to assure high quality results. At the different time points, capillary blood will be collected from mothers and eligible children by experienced technicians trained for the techniques used in this evaluation. For children below 12 months of age, capillary blood will be collected by sticking the heel

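### The child anaemia proportion uses one cut-off, Hb < 11 g/dL, at birth as well as at 6 and 24 months, so anaemia at birth is likely to be near zero and a poor baseline for change (minor, secondary outcome)

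*Protocol*

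**What the plan says.** Protocol section 8.2, blood-based secondary outcomes in study 1 children, begins: "Haemoglobin concentration measured at birth and 6 and 24 months of age will be used to assess the change in haemoglobin concentration". The sentence goes on to the second use of the same measurements, "proportion with anaemia ($Hb < 11g/dL". No other child cut-off is given, and birth is not excluded from the proportion.

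The birth value is actually collected. Section 7.1 says of the newborn at round 3, 24-48 hours after delivery, that "haemoglobin concentration (from a heelprick) will be measured".

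Section 7.3.3 uses a different figure for newborns. A child with low birth weight "and/or has a Hb < 135 g/L, he/she will be referred for a medical check".

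Table 1 in section 5 lists two separate child indicators for study 1: "Change in proportion with anaemia" and "Change in haemoglobin concentration". It gives neither time points nor a cut-off. For repeatedly measured indicators such as child haemoglobin, section 7.2 says: "the average change in outcomes in study subjects in the intervention group will be compared to the average change in study subjects in the control" arm.

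The next sentences of section 8.2 limit the iron deficiency and vitamin A deficiency proportions to 6 and 24 months.

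**The concern.** Read as written, the anaemia proportion is computed at birth with a threshold 25 g/L below the level at which the protocol itself considers a newborn's Hb low enough for a medical check. Three consequences follow.

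- A newborn at 110-134 g/L is referred because of Hb and reported as not anaemic.
- If few newborns fall below 110 g/L, a comparison of anaemia between arms at birth has hardly any events.
- If the change in Table 1 is taken from birth, anaemia in each arm will appear to climb from near zero. A reader would see a steep rise under a hypothesis of reduced prevalence, although most of it would come from age and the cut-off.

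There is a side cost. Section 9.2.4 leaves out of the change analysis any child who lacks one of the paired measurements. With birth as the paired baseline, children without a newborn Hb would be dropped for a baseline value that is nearly constant.

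**Working it through.** The protocol states no prevalence, sample size or power for child anaemia, so there is no figure of its own to reproduce.

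**Units.** 11 g/dL = 110 g/L. The newborn flag is 135 g/L. Difference: 135 - 110 = 25 g/L.

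**Number of newborns.** From section 7.2: 600 women per arm, 95% consent, 80% followed to delivery. 600 × 0.95 × 0.80 = 456 per arm. With the stated design effect of 1.3, the effective number is 456 / 1.3 = 350.8 per arm.

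**Share below each threshold.** Assume newborn Hb is normal with mean m and SD s, where m = 150-170 g/L and s = 15-20 g/L. These values are assumptions; the protocol gives neither. Then P(Hb < c) = Φ((c - m)/s).

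| m | s | P(< 110) | P(< 135) | expected < 110, of 456 |
|---|---|---|---|---|
| 150 | 15 | Φ(-2.67) = 0.4% | Φ(-1.00) = 15.9% | 1.7 |
| 150 | 20 | Φ(-2.00) = 2.3% | Φ(-0.75) = 22.7% | 10.4 |
| 160 | 15 | Φ(-3.33) = 0.04% | Φ(-1.67) = 4.8% | 0.2 |
| 160 | 20 | Φ(-2.50) = 0.6% | Φ(-1.25) = 10.6% | 2.8 |
| 170 | 15 | Φ(-4.00) = 0.003% | Φ(-2.33) = 1.0% | 0.01 |
| 170 | 20 | Φ(-3.00) = 0.1% | Φ(-1.75) = 4.0% | 0.6 |

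The 110-134 g/L band, referred but not counted, is the difference of the two columns: from about 1% (170, 15) to 22.7 - 2.3 = 20.4% (150, 20).

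**Wider range.** With m = 150-180 and s = 15-25, P(< 110) goes up to 5.5% and P(< 135) runs from 0.1% to 27%.

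**Check tied to the protocol's own flag.** Suppose instead that 5-20% of newborns fall below 135 g/L, with s = 15-25. Solving for m gives 0.05-3.3% below 110 g/L, or about 0-15 of 456 per arm.

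**Power at birth for a halving of prevalence** from p to p/2, two-sided 5%, n = 350.8 per arm: Φ( (p/2) / √{[p(1-p) + (p/2)(1-p/2)]/n} - 1.96 ).

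- p = 0.3%: 6%
- p = 1%: 12%
- p = 2%: 0.01/√(0.0295/350.8) = 1.09, and Φ(1.09 - 1.96) = 19%
- p = 5%: 41%

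The normal approximation is rough with so few events, so these figures show only the order of magnitude.

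**Effect on change.** Let B be prevalence at birth and F at follow-up, for arms I and C. The within-arm change is F - B, which is about F when B is near zero, so it mainly shows how common anaemia is at the later age. The between-arm contrast is (F_I - B_I) - (F_C - B_C) = (F_I - F_C) - (B_I - B_C). The last term cannot exceed the larger birth prevalence, so in the main range it is at most 2.3 percentage points. Illustration with assumed figures: 1% at birth in both arms, then 40% and 30%, gives changes of 39 and 29 points. Their difference is 10 points, the same as the follow-up difference.

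**The case against.** Several stronger readings are tempting, and the document does not support them.

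- **Change from birth is uninformative.** A reader might infer this. But section 7.2 plans a comparison of change between arms, and the age-related rise is common to both. As shown above, that contrast approximates the contrast at 6 or 24 months. Only a within-arm change misleads.
- **The haemoglobin change outcome is affected.** It is not. Change in concentration uses no cut-off and is listed separately in Table 1.
- **Sections 7.3.3 and 8.2 contradict each other.** They do not, formally. The 135 g/L figure triggers a medical check and is not called a definition of anaemia. A referral flag may be more sensitive than an outcome definition. What remains is that the protocol uses two unreconciled levels for newborn Hb.
- **Birth is fixed as the baseline for change in anaemia.** It is not. The child sentence in section 8.2 names change in concentration and the proportion with anaemia, not change in that proportion. The latter comes from Table 1, which gives no time points.

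It can also be said that the analysis plan may settle the ages and cut-offs. That has limited force, because section 8.2 has itself fixed both the time points and the single cut-off. It also restricts the iron and vitamin A proportions to 6 and 24 months but not the anaemia proportion.

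Finally, the size rests on a newborn Hb distribution that the protocol does not give. That is correct. In the widest range examined, 5.5% of newborns fall below 110 g/L, which is low but not negligible.

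**Conclusion.** The point holds in a limited form. Section 8.2 applies one cut-off to an outcome that includes birth, and this does not fit the newborn level used in section 7.3.3. Under the assumed mean of 150-170 g/L and SD of 15-20 g/L, anaemia at birth would be about 0-2.3%, while 1-23% of newborns fall below 135 g/L. Power for a halving at birth would be about 6-19% at prevalences of 0.3-2%. Birth prevalence would therefore be nearly empty and a poor starting point for within-arm change, and pairing on it could cost children for almost no information.

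The damage stops there. The between-arm contrast in change, the change in mean Hb and anaemia at 6 and 24 months remain interpretable. The primary length-for-age outcome and its sample size are unaffected. Severity is minor: one time point of one dichotomised secondary outcome.

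**What to change.** In section 8.2, limit the proportion with anaemia at Hb < 11 g/dL, and any change in it, to 6 and 24 months. Add the same time points to the anaemia indicator in Table 1. Analyse birth Hb as a continuous between-arm comparison of means.

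If a proportion at birth is wanted, state a separate newborn-specific analysis definition and explain how it relates to the level in section 7.3.3, so that the two sections are reconciled. This concerns the outcome definition only; the referral rule is not judged here.

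The cost is a few words in section 8.2 and Table 1, carried into the analysis plan. No new data are needed, and no other outcome changes.

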7. STUDY DESIGN AND SAMPLING STRATEGY

7.1 Study design and sampling procedures

Study 1:

General study design: Study 1 is a cluster-randomized, parallel-group, prospective, follow-up effectiveness study over a period of 1000 days comparing 2 groups:

- a) Intervention group: **Pregnant women** will be given LNS (1 sachet/day), raw eggs (2/day), and an anthelmintic drug (albendazole) in the second trimester of pregnancy, as well as soap and chlorine solution for the woman and the household. After delivery these products will be continued until the child reaches 6 months of age. Thereafter, LNS and eggs for mothers and anthelmintic drugs will be discontinued and instead, the **child** will receive LNS (1 sachet/day), one egg/day and Oral Rehydration Salts (ORS) along with zinc tablets (20 mg/day) for treatment in case of acute diarrhoea. These products will be given until the child reaches 2 years of age. The products will be accompanied by life stage-appropriate nutrition and WASH trainings (pregnancy, lactation, infant and young child feeding), as well as SMS reminders to highlight certain messages on antenatal care and nutrition. All products and trainings will be

provided free of charge. The households in the intervention group will also have the same agricultural intervention as the control group.

- b) Control group: All households will be provided with agricultural training (every 2 weeks on average) for free. In addition, households can also enrol for the following products on credit: compost booster, cook stoves, seeds (onions, maize, indigenous greens, beans), maize storage bags, drying tarps, trees, solar lights, fertilizer, actellic dust (insecticide), re-usable sanitary pads.

We anticipate recruiting 1200 (600 in each group) pregnant women into the study (see section 7.2 for sample size calculation); this is expected to yield a sufficiently large sample of children later in the study. Women will be recruited from 120 clusters (randomly assigned to intervention or control) that will be drawn from from Kimilili and Webuye districts in Bungoma County in Western Province of Kenya.

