We anticipate recruiting 1,200 (600 in each group) pregnant women into the study (see section 11.2 for sample size calculation); this is expected to yield a sufficiently large sample of children later in the study. Women will be recruited from 120 clusters (randomly assigned to intervention or control) that will be drawn from from Kimilili and Webuye districts in Bungoma County in Western Province of Kenya.

The communities will be informed about the study in village meetings by CHVs and by conducting outreach within their catchment area to identify pregnant women. Pregnant women will then be screened by 1AF enumerators. During **screening**, a few questions on health status and pregnancy will be asked. If the woman is prior or equal to 20 weeks of gestation (according to last menstrual period), has no visible severe disease and no allergy to peanuts or milk products, and confirms anticipated residence in the area for the coming 30 months, written informed consent for her and her offspring will be sought from her. She will then be asked to provide a urine sample to confirm pregnancy and she will be enrolled if pregnancy is confirmed. Following the screening, 5 assessment rounds (baseline and 4 follow-up assessments during the intervention) will be conducted at the participant's homes (rounds 1-3) or at a central place (rounds 4 and 5) within walking distance from their homes (Figure 2). Assessment round 3 (immediately) after delivery will be conducted as home visits or clinic visits in case of delivery at a clinic. Details of assessment procedures for each round are illustrated in (Figure 3).

Round 1 (Enrolment, ≤ 20 wk of gestation):

On the day of enrolment the round 1 assessment will be done. As part of this, the following information will be collected: household demographics and characteristics, maternal education; knowledge, attitude and practices (KAP) of specific dietary and nutrition practices during pregnancy; individual dietary diversity; antenatal care; WASH practices; height, weight and mid-upper arm circumference; maternal haemoglobin concentration and malaria parasitaemia from a capillary blood sample. After round 1, participants randomly allocated to the intervention group will start receiving the intervention package.

Round 2 (Gestational age of 34 ± 1 wk):

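### Maternal haemoglobin change runs between two visits that both follow the start of the intervention, so any benefit already present at 34 weeks is subtracted from this secondary outcome

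*Protocol*

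**What the plan says.** Section 8.2 of the Protocol, under the blood-based secondary outcomes for pregnant women, states: "Haemoglobin concentration measured at 34 weeks gestation and 6 months postpartum will be used to assess the change in haemoglobin concentration". The same sentence goes on to list the proportion with anaemia and, separately, the change in that proportion.

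Section 7.1 (Study 1) takes a first maternal sample at enrolment, at or before 20 weeks' gestation, for "maternal haemoglobin concentration and malaria parasitaemia from a capillary blood sample". It then says: "After round 1, participants randomly allocated to the intervention group will start receiving the intervention package". Section 8.2 and Table 3 confirm maternal capillary blood at rounds 1, 2 and 4. Round 2 is at 34 ± 1 weeks and round 4 at 6.5 ± 1 months after birth. On the maternal products, section 7.1 says: "After delivery these products will be continued until the child reaches 6 months of age".

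Section 7.2 names maternal haemoglobin among the indicators measured more than once and says: "For these indicators, the average change in outcomes in study subjects in the intervention group will be compared" with the average change in the control group.

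**The concern.** A change score measures a treatment effect when its starting value precedes treatment. Here the starting value, at 34 weeks, has itself been exposed to the intervention, which for these women includes a daily lipid-based supplement containing 20 mg iron (Table 6), eggs and one albendazole dose. If the package raises haemoglobin during pregnancy, that gain enters the starting value in the intervention arm only and is then subtracted.

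At stake is how two maternal secondary outcomes are read: the continuous change in haemoglobin and the change in proportion anaemic. A package that works in pregnancy and keeps its effect would look inert on both. One whose effect partly fades after delivery would look harmful, although intervention mothers were better off at both visits. Anaemia in mothers falls within the Study 1 primary objective (section 4.2), so readers will look at these results.

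**Working it through.** The Protocol gives no sample size or power for maternal haemoglobin, so there is no stated figure to reproduce. The check is algebra on the definition, followed by an illustration.

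**Exposure before round 2.** Latest enrolment is 20 weeks and the earliest permitted round 2 is 33 weeks: 33 − 20 = 13 weeks at the minimum (14 at the nominal visit), and more for women enrolled earlier.

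**What the contrast estimates.** Let the control means at rounds 1, 2 and 4 be m1, m2 and m4. Randomisation makes the arms equal in expectation at round 1. Let the true benefit be d34 at round 2 and d6 at round 4.

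- Control change, round 2 to round 4: m4 − m2
- Intervention change: (m4 + d6) − (m2 + d34)
- Difference between arms: **d6 − d34**
- Anchored on round 1 instead: **d34** at round 2 and **d6** at round 4

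The same algebra applies to the change in proportion anaemic, with risk differences in place of mean differences.

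In g/L, with assumed effects: +5 then +5 gives 5 − 5 = 0; +5 then +3 gives 3 − 5 = −2.

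**Illustration of power.** From section 7.2: 600 women per arm, 95% consent, 80% followed to delivery, design effect 1.3, two-sided alpha 0.05. Effective n per arm = 600 × 0.95 × 0.80 / 1.3 = 351, or 333 if a further 95% continue after delivery. Assumed, not in the Protocol: the effects, and a correlation rho of 0.3 to 0.7 between visits. In units of the single-visit SD, the SD of a change is √(2(1 − rho)). Ranges below cover both values of n and all values of rho; each is the probability of a significant result in the direction shown.

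| Assumed d34, d6 (SD) | Round 4 − round 2 (as defined) | Round 2 − round 1 | Round 4 − round 1 |
|---|---|---|---|
| 0.3, 0.3 | 0.00 (0.025 in favour) | +0.30 (0.905–0.999) | +0.30 (0.905–0.999) |
| 0.3, 0.4 | +0.10 (0.192–0.401) | +0.30 (0.905–0.999) | +0.40 (0.992 or more) |
| 0.3, 0.2 | −0.10 (0.192–0.401, as harm) | +0.30 (0.905–0.999) | +0.20 (0.588–0.928) |
| 0.3, 0 | −0.30 (0.905–0.999, as harm) | +0.30 (0.905–0.999) | 0 |
| 0, 0.3 | +0.30 (0.905–0.999) | 0 | +0.30 (0.905–0.999) |

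The last row marks the limit of the problem: benefit that arises wholly after 34 weeks is captured in full.

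**Does the Protocol repair this elsewhere?** Round 1 haemoglobin is not among the Study 1 baseline variables in section 5, nor among the minimum covariates (socio-economic status, sex, age) in sections 9.2.1 and 9.2.2.

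**Adjustment versus change from round 1.** Adjusting for round 1 multiplies the individual-level variance by 1 − r². At assumed r of 0.4 and 0.6 that is 0.84 and 0.64, a reduction of 16% and 36%. Simple change from round 1 multiplies it by 2(1 − r): 1.2 and 0.8. Both remove the subtraction, but only adjustment is sure not to lose precision.

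**The case against.** The strongest reply is that a pregnancy benefit can be seen elsewhere. Section 8.2 lists the proportion with anaemia as a level, separately from its change, and assesses maternal iron deficiency at 34 weeks as a level. Section 9.2.3 plans an interim comparison between arms of indicators collected during pregnancy, haemoglobin included. All of this stands. A reader might infer from the definition that the maternal anaemia objective would be answered wrongly, or that a benefit in pregnancy would go unseen. The Protocol does not support either reading. What remains is that continuous maternal haemoglobin appears in section 8.2 only as a change, and that the comparison in pregnancy is an interim one and not the main analysis.

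A second reply concerns wording. Section 8.2 is about data collection, does not write out round 4 minus round 2, and could mean change from an unnamed baseline to each visit. Sections 9.2.1 and 9.2.2 leave methods to the SAP and set covariates as a minimum, so adjustment for round 1 is not excluded. That is fair as far as it goes. But the corresponding sentence for children does list its first measurement, at birth, whereas the maternal sentence names exactly two visits and omits the first. The plain reading is 34 weeks to 6 months. This is not a detail left open for the SAP: the Protocol names the visits.

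A third reply is rank. The primary outcome is child LAZ, Table 1 ties the haemoglobin indicators to children, and no power claim rests on maternal haemoglobin. This stands and limits the severity.

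**Conclusion.** The definition is wrong as written for two secondary outcomes: the maternal change in haemoglobin and the change in proportion anaemic. Under section 7.2 both estimate the effect at 6 months postpartum minus the effect at 34 weeks. That result follows from the definition and randomisation alone. The sizes are illustrations on assumed effects: 0.00 SD expected for a benefit of 0.3 SD held at both visits, −0.10 SD if it falls to 0.2 SD. A negative contrast arises only if the benefit shrinks after 34 weeks; a growing benefit shows as positive, though understated.

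Interpretation is harder still because the interval spans pregnancy and the postpartum period, and because the round 4 window (5.5 to 7.5 months) reaches past the point at which maternal products stop.

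The level of anaemia, the interim comparison of haemoglobin in pregnancy and the primary LAZ analysis are unaffected. Should-fix.

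**What to change.** In section 8.2, define the maternal haemoglobin and anaemia effects as between-arm differences at round 2 and at round 4, each adjusted for the woman's round 1 haemoglobin and allowing for clustering. Keep the round 2-to-round 4 change only if labelled descriptive. Add round 1 haemoglobin to the Study 1 baseline variables in section 5, and carry the same definition into the SAP.

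The cost is wording. Round 1 haemoglobin is already scheduled for every enrolled woman in both arms, so no visit, sample or assay is added. The change should be made before the data are analysed.
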